| Sample size calculation | 
The sample size has been calculated to verify equivalence between the test treatment (HFA-152a) and the reference treatment (HFA-134a) for the relative change from baseline in FEV1 at the 15 min post-dose timepoint, with equivalence defined as a difference between the two treatments within the <math>\pm 10\%</math>.
 
A total of 20 evaluable subjects will ensure a 95% power to provide a 95% confidence interval (CI) of the mean difference of the relative change from baseline in FEV1 at 15 min post-dose within the above-mentioned equivalence limits (i.e. [-10%; +10%]) assuming a within-subject standard deviation (SD) of 8%.
 
Estimating a non-evaluable rate of 16%, a total of 24 subjects will be randomised.
  |
| Statistical methods     | 
Safety variables
 
Variable assessing the primary objective of the study (potential for bronchoconstriction of each propellant):
 
 
The relative change from baseline in FEV1 at the 15 min post-dose timepoint will be analysed using an analysis of covariance (ANCOVA) model, including treatment group, subject and period as fixed effects, and FEV1 baseline (mean of the two measurements at 45 min and 15 min pre-dose in each treatment period) as a covariate.
 
 
The adjusted mean relative change from baseline obtained with each treatment and the adjusted mean difference between HFA-152a and HFA-134a with their 95% CIs and p-values will be estimated by the model.
 
Variables completing the evaluation of the potential for bronchoconstriction of each propellant:
 
 
The relative changes from baseline in FEV1 at all the other post-dose timepoints (5 min and 30 min, 1 h, 1 h 30 min and 3 h after T1) will
 
 |

|  |                      |
|--|----------------------|
| Clinical Study Code No.: CLI-05993AB6-07 | Version No.: 2.0     |
| EUDRACT No.: 2022-000536-36              | Date: 30 August 2022 |

|  |  |
|--|--|

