## 4. SUBJECT SELECTION CRITERIA

### 4.1 Subject Recruitment

Subjects attending the hospital clinics/study centres will be recruited. Adult male and female subjects with mild asthma (Step 1 of the GINA 2021 guidelines), aged from 18 to 75 years old (inclusive) will be selected.

A total of 24 subjects will be randomised in accordance with the inclusion and exclusion criteria, in order to reach a total of 20 completed and evaluable subjects, considering a non-evaluable rate of approximately 16%.

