#### 6.2.3.1 Administration with Pressurised Metered Dose Inhaler

The study treatment will be administered by inhalation using the pMDI device, according to the following instructions:

- **Position:** subjects must be in an upright position;
- **Duration of treatment administration:** the [REDACTED] inhalations should be performed within 12 min;

|  |                      |
|--|----------------------|
| Clinical Study Code No.: CLI-05993AB6-07 | Version No.: 2.0     |
| EUDRACT No.: 2022-000536-36              | Date: 30 August 2022 |

- **T0** is defined as the moment when the first inhalation takes place, and will be used to calculate the pre-dose timepoints;
- **T1** is defined as the moment when the last [redacted] inhalation takes place, and will be used to calculate the post-dose timepoints.

Subjects performing the [redacted] inhalations in more than 12 min will be considered as protocol deviations;

- **Time between two consecutive inhalations:** two consecutive inhalations must be separated by 40 seconds minimum, during which subjects must:
  - Hold their breath for the 10 seconds following the inhalation;
  - Wait approximately 30 seconds before taking the next inhalation.

If a subject coughs during the [redacted] inhalations, the Investigator must wait until the cough is resolved and then resume treatment administration. If the cough is severe and does not resolve spontaneously, the subject must stop treatment intake in the interest of his/her safety. The appropriate measures should be taken.

An incorrect inhalation is defined as “a significant reduction of delivered dose that reaches the lungs based on Investigator or designee judgement”. Even if this is the case, no extra inhalations (i.e. more than the [redacted] inhalations required) will be administered.

Treatment administration will be recorded in the eCRF by the Investigator or designee. Any issues occurring during the inhalations as evaluated by the Investigator or designee will be reported in the eCRF.

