## 12. STATISTICAL METHODS

### 12.1 Sample Size

The sample size has been calculated to verify equivalence between the test treatment (HFA-152a) and the reference treatment (HFA-134a) for the relative change from baseline in FEV1 at the 15 min post-dose timepoint, with equivalence defined as a difference between the two treatments within the 10% (i.e. [-10%; +10%]).

A total of 20 evaluable subjects will ensure a 95% power to provide a 95% confidence interval (CI) of the mean difference of the relative change from baseline in FEV1 at 15 min post-dose within the above-mentioned equivalence limits (i.e. [-10%; +10%]) assuming a within-subject standard deviation (SD) of 8%.

Estimating a non-evaluable rate of 16%, a total of 24 subjects will be randomised.

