### 12.2 Populations for Analysis

- **Safety population:** all randomised subjects who receive at least one dose of any of the two study treatments (analysed as treated);
- **Per-protocol population (PP):** all subjects from the Safety population, except those subjects with important protocol deviations impacting the analysis population. Exact definition of important protocol deviations impacting the analysis population will be discussed by the study team during the blind review of the data and described in the Data Review Report.

Since a cross-over design will be used, the inclusion in the populations for analysis will be defined on a per-period basis.

The Safety population will be used for the analysis of all safety variables. The variables assessing the primary study objective will also be analysed considering the PP population, for sensitivity purposes.

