### 12.3.6 Safety Variables

Safety analyses will be based on the Safety population. For sensitivity purposes, the safety variables assessing the primary objective of the study will also be analysed in the PP population (see [Section 12.2](#)).

The safety variables of the study are presented in [Section 9](#).

The safety variable assessing the **primary objective** of the study (i.e. evaluation of the potential for bronchoconstriction of each propellant) will be analysed as follow:

- The relative change from baseline in FEV1 at the 15 min post-dose timepoint will be analysed using an analysis of covariance (ANCOVA) model, including treatment group, subject and period as fixed effects, and FEV1 baseline (mean of the two measurements at 45 min and 15 min pre-dose in each treatment period) as a covariate. The adjusted mean relative change from baseline obtained with each treatment and the adjusted mean difference between HFA-152a and HFA-134a with their 95% CIs and p-values will be estimated by the model.

The other safety variables completing the evaluation of the potential for bronchoconstriction of each propellant will be analysed as follows:

- The relative changes from baseline in FEV1 at all the other post-dose timepoints (5 min, 30 min, 1 h, 1 h 30 min and 3 h after T1) will be analysed using the same model used for the relative change from baseline in FEV1 at 15 min post-dose;
- The absolute changes from baseline in FEV1 at all post-dose timepoints (5 min, 15 min, 30 min, 1 h, 1 h 30 min and 3 h after T1) will be analysed using the same model used for the relative change from baseline in FEV1 at 15 min post-dose;
- The number and percentage of subjects with a relative change from baseline in FEV1 at each post-dose timepoint (5 min, 15 min, 30 min, 1 h, 1 h 30 min and 3 h after T1) and at any post-dose timepoint <-15% will be summarised for each treatment;
- The change from baseline in FEV1 AUC0-3h will be summarised using descriptive statistics;
- The relative and absolute changes from baseline in PEF at all post-dose timepoints (5 min, 15 min, 30 min, 1 h, 1 h 30 min and 3 h after T1) will be summarised for each treatment, using descriptive statistics;
- The number and percentage of subjects with use of rescue medication in the 3 h post-dose will be summarised for each treatment;

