5. GENERAL METHODOLOGY

5.1 ANALYSIS SETS

5.1.1 *Analysis sets*

The following analysis sets will be considered in the statistical analysis:

Enrolled Set (ENR): subjects who *signed an informed consent* to participate in this study

Randomised Set (RND): subjects who were *randomised* into this study

Safety Set (SAF): subjects who were randomised and *received at least one dose of study drug*

Per Protocol (PP) Analysis Set: subjects from the SAF, excluding the subjects having important protocol deviations impacting the analysis set

Notes:

- Having signed an informed consent is defined as having a complete informed consent signature date in the database.
- Randomised is defined as having a randomisation date in the database or any information to confirm randomisation.
- Having received at least one dose of study drug is defined as having an exposure date or any information confirming exposure.
- Exact definition of important protocol deviations concerning PP will be discussed by the clinical team and described in the DRR. The subjects to be excluded from PP analysis set will be defined in the DRR.

Unless stated otherwise, the SAF will be used for the general characteristics, safety [REDACTED] tables, listings and figures. The variables assessing the primary study objective will also be analysed considering the PP, for sensitivity purposes.

Since a cross-over design will be used, the inclusion in the analysis sets will be defined at subject level on a per-period basis and at subject level overall (in case all periods are affected). In case of important protocol deviations impacting specific time points, only the affected data at the specific time point will be excluded from the applicable analysis sets. These cases will be documented in the DRR.

5.1.2 *As planned versus as actual analysis*

For analyses done on the safety analysis set and on PP analysis set (excluding general characteristics analyses), the actual treatment of the subject will be considered. In addition, the actual treatment will be presented in all listings.

For all other analyses, the planned treatment (sequence) will be used.

	Statistical Analysis Plan	
CLI-05993AB6-07		Final 1.0 of 22DEC2022

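### The trial is sized for equivalence in 20 evaluable subjects, but its primary analysis uses everyone dosed, per-protocol is only a sensitivity check, and no rule says which set decides.

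*Protocol*

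**What the plan says.** **Sizing.** Protocol Outline (Sample size calculation), Protocol 12.1 and SAP 1.3 size the study to verify equivalence of HFA-152a and HFA-134a on relative change from baseline in FEV1 at 15 minutes, with limits [-10%; +10%] and a within-subject SD of 8%: "A total of 20 evaluable subjects will ensure a 95% power to provide a 95% confidence interval (CI) of the mean difference" lies within the limits. A 16% non-evaluable rate takes 20 to 24 randomised. Protocol 4.1 describes the target as "in order to reach a total of 20 completed and evaluable subjects". Neither document ties 'evaluable' to an analysis set.

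**Analysis set.** Protocol 12.2 states: "The Safety population will be used for the analysis of all safety variables". That population is every randomised subject who received at least one dose, as treated. Protocol 12.3.6 adds: "For sensitivity purposes, the safety variables assessing the primary objective of the study will also be analysed in the PP population". SAP 5.1.1 agrees: "The variables assessing the primary study objective will also be analysed considering the PP, for sensitivity purposes". In SAP 8.1, Table 14.3.7.3.1 carries the primary-objective title on the Safety set. Table 14.3.7.3.2 repeats the ANCOVA on PP.

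**Decision rule.** Protocol 12.3.6 and SAP 2.5.3 ask for the adjusted difference, its 95% CI and a p-value. Neither restates the ±10% limits or says how the Safety and PP results combine.

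**Who stays in the Safety set.** Protocol 6.2.3.1 defines an incorrect inhalation as "a significant reduction of delivered dose that reaches the lungs based on Investigator or designee judgement" and allows no extra inhalations. It also has dosing stop for severe cough that does not resolve. These subjects remain in the Safety set. Both documents leave the deviations that remove a subject from PP to the blind data review.

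**The concern.** In a superiority trial, analysing everyone dosed is usually the cautious choice, because deviations shrink the difference and make the claim harder. In an equivalence trial the same shrinkage helps the claim. A subject measured in both periods whose contrast between propellants is blunted adds a difference nearer zero. That can happen if the lung dose was reduced in both periods, or in the period of the worse propellant, or if a wash-out breach went uncorrected and left the airway bronchodilated.

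This matters because of why the trial exists. Protocol 1.2 says earlier studies could not assess bronchoconstriction because the propellant was given with bronchodilating agents. A deciding set that keeps bronchodilated or under-dosed subjects, with no agreed role for PP, recreates part of that weakness.

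**Working it through.** **Inputs.** Margin 10 points, within-subject SD 8, 95% CI (2.5% per side), 20 evaluable, 24 randomised, 16% non-evaluable (Protocol 12.1, SAP 1.3); two-sequence, two-period cross-over (Protocol 6.5). Assumed because the documents do not state them: a true difference of 0 for power, and the number and degree of diluted subjects.

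**Reproducing the plan's figure.** The standard error of the treatment difference is SE = 8 × √(2/n).

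- n = 20: SE = 8 × √0.1 = 2.53. By the normal approximation, power = 2Φ(10/2.53 − 1.96) − 1 = 2Φ(1.99) − 1 = 95.4%. This matches the stated 95%, and 20 is the smallest n that reaches it.
- 20/(1 − 0.16) = 23.8, rounded up to 24. Conversely, 24 × 0.84 = 20.2.
- With a t-based CI on n − 2 degrees of freedom, n = 20 gives 92.4%, n = 22 gives 95.2% and n = 24 gives 97.0%.

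The sample size is therefore reproducible. The question is which subjects it refers to.

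**False equivalence on the Safety set.** Take 24 subjects with both periods and a true difference of exactly 10 points, so a correct procedure concludes equivalence 2.5% of the time. If k subjects show no contrast, the mean difference becomes 10 × (1 − k/24): 9.58, 9.17 and 8.33 for k = 1, 2 and 4. If the CI kept its nominal width, false equivalence would be 3.7%, 5.3% and 10.2%.

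The diluted subjects also make the individual differences more variable, which widens the CI. For k = 4 the expected variance of the differences rises from 2 × 8² = 128 by about 10² × 4 × 20/(24 × 23) = 14.5. A simulation that includes this (200,000 replicates, period-adjusted t-based CI) gives the more cautious figures below. PP is taken as the Safety set minus exactly the k diluted subjects.

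| Affected of 24 | Safety, no contrast left | Safety, half the contrast left | Both sets required |
|---|---|---|---|
| 0 | 2.5% | 2.5% | 2.5% |
| 1 | 3.4% | 3.0% | 2.2-2.4% |
| 2 | 4.7% | 3.6% | 2.1-2.4% |
| 4 | about 8.5% | 5.1% | 2.1-2.4% |

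**Limits of the illustration.**

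- Four diluted subjects at a true difference of 12 points give 1.8%; at 14 points, 0.2%. The inflation matters near the margin.
- If four subjects instead carry 1.2 times the effect, as when the dose is reduced in the period of the better propellant only, false equivalence on the Safety set falls to about 1.8%.
- If PP keeps the diluted subjects, requiring both sets protects nothing and the rate with four of them is again about 8.5%.

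**Power at zero true difference.** Safety set with n = 24: 97.0%. PP with n = 20: 92.4%. Both required: 91.9%.

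**The case against.** The other side has real strength.

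- **There is no stated rule to criticise.** A reader might infer that the plan lets equivalence be declared on the Safety set even if PP fails. The documents do not say so; they give no decision rule at all outside the sample-size text. What stands is the gap, not a permissive rule.
- **PP is already planned and visible.** The same ANCOVA is specified on PP, and both tables are flagged as key first results. The endpoint is a safety variable, so the Safety set is an understandable default. But that label does not change the hypothesis, which the plan states as equivalence.
- **Some deviations are handled.** Restrictions are checked before dosing, and a visit in breach should be rescheduled once (Protocol 7.3.1). Subjects who fail inhaler training are not included (Protocol 6.2.4.1). SAP 5.1.1 and 5.3.5 let the data review exclude affected time points or outliers. This lowers the likely number of diluted subjects, but no criteria for under-dosing or a failed wash-out are set in advance.
- **The direction is not fixed.** A reader might infer that the Safety set always favours equivalence. It does not: a deviation confined to the period of the better propellant enlarges the difference, and a subject with one period adds almost nothing when subject is a fixed effect.
- **PP is not reliably the cautious set.** Subjects who stopped dosing for cough may be the reactive ones, and PP could drop them. This stands, and it argues against making PP alone primary.

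**Conclusion.** The point holds as a mismatch and a missing rule. The trial is sized on evaluable subjects, the primary analysis is on all dosed subjects, and the documents do not say what is concluded if the Safety and PP results disagree. The sample-size arithmetic is not in error.

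The size is modest and conditional. With a true difference exactly on the margin, SD 8 and both periods observed, one or two affected subjects of 24 give a false-equivalence rate of about 3-5% instead of 2.5%. A reader might take about 8.5% as the expected rate, because four of 24 is close to the plan's 16%. The documents do not support that: Protocol 4.1 speaks of completed and evaluable subjects, so the 16% includes drop-outs, and no document gives a rate of under-dosing or wash-out breach. It is a worst case. The change is worth making before unblinding because it is cheap and bears on the primary conclusion.

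**What to change.** 1. In Protocol 12.2 and 12.3.6 and SAP 2.5.3 and 5.1.1, state that equivalence is concluded only if the 95% CI for HFA-152a minus HFA-134a lies within [-10%; +10%] in both the Safety set and the PP set. Label Tables 14.3.7.3.1 and 14.3.7.3.2 as jointly primary.
2. Before unblinding, fix in the SAP which deviations remove a subject-period from PP for this analysis. Examples are incorrect or incomplete inhalations, an uncorrected SABA, ICS or ICS-formoterol wash-out breach, and rescue medication before the 15-minute reading. Without this step the joint rule does not secure its protection.
3. Report separately the subjects who stopped dosing for cough or bronchospasm, since PP may remove reactive subjects.
4. State that the 20 evaluable subjects are PP subjects with both periods.

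**Cost.** Protocol and SAP wording only; both tables already exist and N stays at 24. Power at zero true difference falls from about 97% (Safety set, n = 24) to about 92% (both sets, PP n = 20), so the stated 95% should be restated.

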## LIST OF ABBREVIATIONS AND DEFINITION OF TERMS

|                           |   |
|---------------------------|---|
| ACQ-5              | Asthma Control Questionnaire ®                         |
| ADR                | Adverse Drug Reaction   |
| AE                 | Adverse Event   |
| ALT                | Alanine Aminotransferase  |
| ANCOVA             | Analysis of Covariance  |
| AST                | Aspartate Aminotransferase  |
| ATC                | Anatomical Therapeutic Chemical                                   |
| ATS                | American Thoracic Society   |
| AUC                | Area Under the Concentration-Time Curve                           |
| AUC0-3h | Area Under the Concentration-Time Curve from Time Zero to 3 Hours |
| BTPS               | Body Temperature and Pressure Saturation                          |
| Ca                 | Calcium   |
| CHMP               | Committee for Medicinal Products for Human Use                    |
| CI                 | Confidence Interval   |
| CIOMS              | Council for International Organizations of Medical Sciences       |
| Cl                 | Chloride Electrolyte  |
| COPD               | Chronic Obstructive Pulmonary Disease                             |
| COVID-19           | Coronavirus Disease 2019  |
| CRO                | Contract Research Organisation                                    |
| CS                 | Clinically Significant  |
| DALY               | Disability Adjusted Life Year                                     |
| DBP                | Diastolic Blood Pressure  |
| DPI                | Dry Powder Inhaler  |
| EC                 | Ethics Committee  |
| ECG                | Electrocardiogram   |
| eCRF               | Electronic Case Report Form                                       |
| EMA                | European Medicines Agency   |
| ERS                | European Respiratory Society                                      |
| FEV1    | Forced Expiratory Volume in 1 Second                              |
| FSH                | Follicle-Stimulating Hormone                                      |
| FVC                | Forced Vital Capacity   |
| γ-GT               | Gamma-Glutamyl Transpeptidase                                     |
| GCP                | Good Clinical Practice  |
| GINA               | Global Initiative for Asthma                                      |
| GMP                | Good Manufacturing Practice                                       |

|  |                      |
|--|----------------------|
| Clinical Study Code No.: CLI-05993AB6-07 | Version No.: 2.0     |
| EUDRACT No.: 2022-000536-36              | Date: 30 August 2022 |

|                |  |
|----------------|--|
| GOLD    | Global Initiative for Chronic Obstructive Lung Disease |
| GWP     | Global Warming Potential                               |
| h       | Hour   |
| Hb      | Haemoglobin  |
| Hct     | Haematocrit  |
| HFA     | Hydrofluoroalkane                                      |
| HR      | Heart Rate   |
| ICF     | Informed Consent Form                                  |
| ICH     | International Council for Harmonisation                |
| ICS     | Inhaled Corticosteroid                                 |
| ICSR    | Individual Case Study Report                           |
| IgE     | Immunoglobulin E                                       |
| IgG     | Immunoglobulin G                                       |
| K       | Potassium  |
| LABA    | Long-Acting $\beta$ 2-Agonist                          |
| LAMA    | Long-acting anti-muscarinic                            |
| LTRA    | Leukotriene receptor antagonist                        |
| MedDRA  | Medical Dictionary for Regulatory Activities           |
| MHRA    | Medicines and Healthcare Products Regulatory Agency    |
| min     | Minute   |
| Na      | Sodium   |
| No.     | Number   |
| NYHA    | New York Heart Association                             |
| PEF     | Peak Expiratory Flow                                   |
| PK      | Pharmacokinetic  |
| PLT     | Platelet   |
| pMDI    | Pressurised Metered Dose Inhaler                       |
| PP      | Per-Protocol   |
| PR      | PR Interval  |
| PT      | Preferred Term   |
| QRS     | QRS Interval   |
| QTcF    | QT Interval Corrected Using Fridericia's Formula       |
| RBC     | Red Blood Cell   |
| R&D | Research and Development                               |
| SABA    | Short-Acting $\beta$ 2-Agonists                        |
| SAE     | Serious Adverse Event                                  |

|  |                      |
|--|----------------------|
| Clinical Study Code No.: CLI-05993AB6-07 | Version No.: 2.0     |
| EUDRACT No.: 2022-000536-36              | Date: 30 August 2022 |

|               |   |
|---------------|---|
| SAP    | Statistical Analysis Plan                       |
| SBP    | Systolic Blood Pressure                         |
| SD     | Standard Deviation                              |
| SOC    | System Organ Class                              |
| SUSAR  | Suspected Unexpected Serious Adverse Reaction   |
| T0     | Time of First Inhalation of the Study treatment |
| T1     | Time of Last Inhalation of the Study treatment  |
| TEAE   | Treatment-Emergent Adverse Event                |
| TP     | Treatment Period                                |
| UK     | United Kingdom                                  |
| WBC    | White Blood Cell                                |
| WHO    | World Health Organization                       |
| WOCBP  | Women of Childbearing Potential                 |
| WONCBP | Women of Non-Childbearing Potential             |

|  |                      |
|--|----------------------|
| Clinical Study Code No.: CLI-05993AB6-07 | Version No.: 2.0     |
| EUDRACT No.: 2022-000536-36              | Date: 30 August 2022 |

